### 5.4.1.4. Missing Data

Missing data will not be imputed. Participants who do not report an event will be considered as participants without an event. An AE with a missing severity or relationship will be considered as an AE reported, but will be considered as not reported for the severity or relationship. For example, an AE with missing severity will be considered as an AE reported for the analysis of any grade but will be considered as not reported for the analysis of at least grade 3. The analysis of solicited AEs will include the safety data as documented by the investigator.

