9.4.4. Safety Analyses

No formal statistical testing of safety data is planned. Safety data (including solicited and unsolicited AEs) will be analyzed descriptively by cohort and group. All safety analyses will be based on the FA Set.

AEs

The verbatim terms used in the eCRF by investigators to identify AEs will be coded using the Medical Dictionary for Regulatory Activities (MedDRA). All reported AEs with onset during the active phase (ie, AEs occurring from the time of vaccination up to 28 days post-vaccination), and all SAEs and AESIs will be included in the analysis. For each AE, the number and percentage of participants who experience at least 1 occurrence of the given event will be summarized by group.

Summaries, listings, datasets, or participant narratives may be provided, as appropriate, for those participants who die, who discontinue study vaccination due to an AE, or who experience a severe AE, an SAE, or an AESI.

Summaries and/or listings may be provided separately for AEs with onset outside the above defined timeframe (ie, beyond 28 days post-vaccination).

Solicited local (injection site) and systemic AEs will be summarized descriptively. The overall frequencies per group as well as frequencies according to severity and duration will be calculated for solicited AEs. In addition, the number and percentages of participants with at least 1 solicited local (injection site) or systemic AE will be presented. Frequencies of unsolicited AEs, separately for all and vaccination-related only, will be presented by System Organ Class and preferred term.

Vital Signs

Baseline and emerging vital signs abnormalities will be listed.

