# 5.4. Primary Safety Endpoint Analysis

Safety endpoints include:

- Solicited local (injection site) and systemic AEs for 7 days after vaccination
- Unsolicited AEs for 28 days after vaccination
- Serious adverse events (SAEs) and adverse events of special interest (AESIs) until 6 months after vaccination

No formal statistical testing of safety data is planned. Safety data will be analyzed descriptively by cohort and group. All safety analyses will be based on the FA Set. Continuous variables will be summarized using the following statistics, as appropriate: number of observations, median, minimum and maximum. Frequencies and percentages (one decimal place) will be generated for categorical variables.

Safety data will be analyzed by study intervention regimens as designed per protocol, per phase and across the entire study period where applicable. For unsolicited AE, denominator for the percentages is the number of participants in the considered population and phase for a certain regimen (incidence per 100 participants/phase). For solicited AEs, the denominator for the percentages is the number of participants with data assessed by the PI in the considered population and phase for a certain and phase for a certain regimen (incidence per 100 participants/phase).

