# 5.4.1.2. Analysis of Adverse Events

Number and percentage of participants with at least one particular AE (unsolicited/solicited) will be tabulated. Unsolicited AEs will be summarized by System Organ Class and Preferred Term. Solicited AEs will be summarized by class (administration site, systemic) and preferred term. AESI will be summarized by Interest Category and Preferred Term.

For solicited AEs, the following tables will be provided: summary, by worst severity grade, at least grade 3, related (systemic only), time to onset (in days) and duration (in days). Note: Duration is defined as number of days from the start of the event until resolution of the event. The time to first onset is defined as (date of first onset – reference date + 1). The reference date is the start date of the post-dose period.

For unsolicited AEs following tables will be provided: summary table (including SAE, fatal outcome, AESI, AE leading to study discontinuation), all events, most frequent, at least grade 3, related, AE leading to study discontinuation, related, SAE, and related SAE.

Moreover, table with Covid AEs, potential AESI as identified by the investigator, potential AESIs selected programmatically and potential AESI qualified for assessment will be created.

Potential AESIs selected programmatically will be tabulated by categories: 'Embolic and thrombotic events (SMQ)' and 'Haematopoietic Thrombocytopenia (SMQ) (broad) or HLT = Thrombocytopenias'. Potential AESI determined programmatically, related to study vaccine (investigator assessment), will be tabulated similarly.

Potential AESIs as identified by the investigator, will be tabulated by categories: '*Embolic and thrombotic events (SMQ)*' and '*Haematopoietic Thrombocytopenia (SMQ)* (broad) or HLT = Thrombocytopenias', and 'Other'. Potential AESI as identified by the investigator, related to study vaccine (investigator assessment), will be tabulated similarly.

Potential AESIs qualified for assessment will be tabulated by categories: 'Embolic and thrombotic events (SMQ)' and 'Haematopoietic Thrombocytopenia (SMQ) (broad) or HLT = Thrombocytopenias'

All AESI analyses will be presented by phase as well as by time interval. The definition of the different time intervals can be found in Section 5.1.2.

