# 5.7.1. Data Monitoring Committee (DMC) or Other Review Board

An IDMC will be installed to monitor the safety of participants in the ongoing phase 3 studies.

There are no planned IDMC reviews in the current study. Safety issues that might arise from this study may be escalated to an IDMC.

If a safety issue arises, the team might request an adhoc safety review by the IDMC. This review would be based on a snapshot of the database which might not have been completely cleaned. Data will be cleaned on an ongoing basis. The IDMC will review unblinded data; the data package to be reviewed (summary data) will display the real vaccine identity. The study team will transfer the blinded data to the statistical support group (SSG), and the IWRS vendor or Secure Data vendor will securely transfer the unblinded randomization data to the SSG. In principle there will be no meeting, unless this is requested by one of the IDMC members or by the Sponsor.

Conclusions from the IDMC reviews will be communicated to the Sponsor.

The IDMC data package (summary data) will follow the same statistical methods described in this SAP. Depending on the safety issue, the IDMC data package will consist of one or more of the following tabulations: participant disposition and demographics, SAEs, related SAEs, fatal AEs, related fatal AEs, solicited and unsolicited grade 3 AEs and related AEs. Potential AESI qualified for assessment will be listed. Other safety summaries might be requested as well. A separate IDMC DPS document will be provided to describe the specifications of the individual tables to be generated should a safety issue arise.

Data packages will be distributed by the SSG to the IDMC members via a secure electronic environment. A separate data package might be made available to the study team where the summary data are presented for the pooled groups (blinded).

The roles and responsibilities of the IDMC and SSG are detailed in the IDMC charter (Section 5).

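### AEs with missing relationship or severity are left out of the related and grade 3-or-higher tables, which within a group can only lower those counts

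*SAP*

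**What the plan says.** The rule is in SAP 5.4.1.4: "An AE with a missing severity or relationship will be considered as an AE reported, but will be considered as not reported" for whichever attribute is missing. The section's own example settles the reading: "an AE with missing severity will be considered as an AE reported for the analysis of any grade", but it "will be considered as not reported for the analysis of at least grade 3". By the same sentence, an AE with no recorded relationship is absent from every table restricted to related events.

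SAP 5.4.1.2 lists the unsolicited tables as a summary table plus "all events, most frequent, at least grade 3, related, AE leading to study discontinuation, related, SAE, and related SAE". It also plans at-least-grade-3 and related tables for solicited AEs (related for systemic events only), and related tables for potential AESIs, both those identified by the investigator and those selected by program. Protocol 9.4.4 makes a matching commitment: "Frequencies of unsolicited AEs, separately for all and vaccination-related only, will be presented".

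SAP 5.7.1 says an ad hoc IDMC package uses the SAP's methods. Its possible contents include related SAEs, related fatal AEs, grade 3 AEs and related AEs. On the data behind it: "This review would be based on a snapshot of the database which might not have been completely cleaned".

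Neither document plans a count of AEs with a missing attribute or a sensitivity analysis of the rule.

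**The concern.** An event whose relationship or grade is unknown might or might not belong in a restricted table. The rule settles every such case by leaving the event out, and no footnote tells the reader. A zero in the related SAE row could therefore mean that every SAE was judged unrelated, or that one has not yet been judged.

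The SAP is more cautious elsewhere. An AE with a completely missing start date goes to the post-dose period unless its end date shows otherwise (SAP 5.4.1.3), and a vital-sign abnormality with no baseline always counts as emerging (SAP 5.4.2). Section 5.4.1.4 goes the other way without giving a reason.

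The IDMC package is where this matters most. It would be produced because a safety issue had arisen, at a time when attributes may still be pending. A death awaiting a causality assessment would appear among the fatal AEs but not among the related fatal AEs.

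**Working it through.** **Which tables the rule reaches**

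| Output | Missing relationship | Missing severity |
|---|---|---|
| All AEs, SAEs, fatal AEs, AESIs | still counted | still counted |
| Related AE, related SAE, related potential AESI, related fatal AE (IDMC) | left out | no effect |
| At least grade 3 | no effect | left out |

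The primary safety endpoints in SAP 5.4, for example "Unsolicited AEs for 28 days after vaccination", are in the first row.

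**The plan's own safety figures.** Protocol Table 6 uses P(at least one event) = 1 − (1 − p)^n. At true rates of 0.5%, 1% and 2.5%, n = 315 gives 0.7938, 0.9578 and 0.9997, and n = 630 gives 0.9575, 0.9982 and 1.0000. These match the stated 79%, 96%, 100% and 96%, 100%, 100%. The zero-event one-sided 95% upper limit, 1 − 0.05^(1/n), is 0.947% at 315 and 0.474% at 630, which matches the stated limits of below 1% and below 0.5%.

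**Effect of the rule within a group.** Let p be the true rate of a restricted event and m the share with the attribute missing, taking one event per participant and missingness unrelated to the true class. The tabulated rate is p(1 − m), never above p. If every missing attribute is counted as qualifying, and a is the any-AE rate, the tabulated rate is p(1 − m) + a·m. The documents give no value for p, a or m. Assume a = 30% and p = 3%:

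| m | SAP rule | All missing counted as qualifying |
|---|---|---|
| 1% | 2.97% | 3.27% |
| 2% | 2.94% | 3.54% |
| 5% | 2.85% | 4.35% |
| 10% | 2.70% | 5.70% |

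With n = 315 and a true rate of 1%, the chance that the restricted table shows at least one event falls from 95.8% to 95.1%, 94.2% and 92.0% when m is 5%, 10% and 20%.

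**A single SAE.** With no recorded relationship in an active group of 315, it shows as 0 (0.0%) instead of 1 (1/315 = 0.3%) in the related SAE row. The exact one-sided 95% upper limits would be 0.95% and 1.50%, but the SAP plans no such limit for this row.

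**Between groups.** Assume true rates of 3% active and 1% placebo (difference 2.0 points, ratio 3.0):
- 10% missing in both: 2.7 − 0.9 = 1.8 points, ratio 3.0.
- 10% missing in active only: 2.7 − 1.0 = 1.7 points, ratio 2.7.
- 10% missing in placebo only: 3.0 − 0.9 = 2.1 points, ratio 3.33.

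The direction is fixed within a group but not for the comparison.

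**The case against.** The strongest reply is that the rule imputes nothing. It does not label an event unrelated or mild. It leaves the event unclassified and keeps it in the overall tables, where the primary endpoints are read. Protocol 10.2.5 requires investigators to record their causality opinion, and SAE forms must be completed and reviewed by a site physician and sent within 24 hours (Protocol 8.3.1). Local solicited AEs are related by definition (SAP 5.4.1.1), and erythema, swelling and fever are graded from measurements (Protocol 10.2.3). SAP 5.4.1.2 provides listings or narratives, as appropriate, for serious events. No IDMC review is planned, data are cleaned on an ongoing basis, and the possible package also covers SAEs and fatal AEs whatever their causality.

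Most of this stands and keeps the point small. It does not remove the one-way effect in the restricted tables, and a field that must be completed can still be empty in a snapshot.

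Three stronger readings are tempting, and the documents do not support them:
- *The primary safety result is flattered.* The occurrence endpoints still count these events. The zero-event statement in Protocol 9.2.2 concerns events in the database, and these events are there.
- *Every gap in the data favours the vaccine.* The start-date and vital-sign rules run the other way. SAP 5.4.1.4 does also say "Participants who do not report an event will be considered as participants without an event", but that is a separate rule about people with no report.
- *The comparison always favours the vaccine.* A gap in the placebo group makes the vaccine look worse, as shown above.

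The objection also holds against counting every missing severity as at least grade 3 in the main table. At 5% missing that overstates the assumed 3% by 1.35 points, whereas the SAP rule understates it by 0.15.

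**Conclusion.** The point holds for the restricted tables only. Missing relationship or severity can only lower the related and at-least-grade-3 counts within a group, the reader is not told how many events are involved, and the same rule would carry into an ad hoc IDMC package. AE, SAE and AESI occurrence is unaffected, and no sample size, power or alpha depends on the rule.

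The size is a proportional loss of m in each restricted rate: 0.03 to 0.30 points on an assumed 3% for 1% to 10% missing. In rows with very few events it may be the difference between none and one. That few records will be affected in clean final data is an expectation based on the recording requirements, since the documents give no missing rate. For a snapshot the number is unknown. This is a minor improvement to the plan, not a threat to its conclusions.

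**What to change.** Amend SAP 5.4.1.4 before unblinding:

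1. Count an AE with missing relationship as related in all related tables, including related SAE, related potential AESI and related fatal AE.
2. Keep an AE with missing severity unclassified in the main at-least-grade-3 table, and add one sensitivity table that counts it as at least grade 3.
3. Footnote, by group, the number of AEs with missing relationship and the number with missing severity.
4. State in SAP 5.7.1 that items 1 to 3 also apply to IDMC packages.

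The cost is a few lines of text and programming and one extra table. The related rates may be slightly less favourable, in active and placebo alike. One recoded event adds 1/315 = 0.3% in an active group, 1/70 = 1.4% in a Cohort 1 or 2 placebo group, and 1/28 = 3.6% in the Cohort 3 placebo group. If many relationships were missing, item 1 would overstate the related rate as in the last column of the rate table. The footnote lets the reader see this and subtract those events.

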# 5.4.2. Vital Signs

Baseline and emerging vital sign abnormalities will be listed based on the abnormality gradings in Appendix 5. An abnormality will be considered as emerging if it is worse than the baseline value. If the baseline is missing, the abnormality is always considered emerging.

# 5.5. Secondary and Exploratory Immunogenicity Endpoints Analysis

# 5.5.1. Secondary and Exploratory Immunogenicity Endpoint(s)

Humoral and cellular immune responses against the insert are measured. The measured humoral immune responses include titers of neutralizing antibodies and binding antibody titers (ELISA). The measured cell-mediated immune responses include RSV specific INF $\gamma$  ELISpot responses and intracellular cytokine staining (ICS) if available. Immunogenicity against the vector will be explored using an adenovirus neutralization assay.

Immunogenicity responses will be summarized per cohort and group.

Note: Exploratory endpoints are optional. Exploratory assessments are based on the outcome of ongoing testing in other studies. Some testing may not be performed or reported.

# 5.5.1.1. Handling of Missing and/or Unquantifiable Immune Response Data

Missing immune response data will not be imputed.

Values below the lower limit of quantification (LLOQ) will be treated differently according to the assay:

- For all humoral assays, the same rules as described in Section 5.3.3 will be used.
- For ELISpot assays: the LLOQ will be used if available and validated, the same rules as described in Section 5.3.3 will be used.
- For ICS assays: the LLOQ will be used if available and validated. In case no validated LLOQ is available then a provisional cut-off will be provided before DBL (only for total cytokine response), in the database. The same rules as described in Section 5.3.3 will be used. For the individual cytokine combinations of IFNγ, TNFa and IL2, if available, negative values will be imputed with 0.

Data above the ULOQ will be imputed with the ULOQ.

### 5.5.1.2. Immunogenicity Against the Insert:

#### 5.5.1.2.1. Humoral assays

For VNA and ELISA assays following results will be calculated: N, geometric mean§ and corresponding 95% CI of the actual values and fold increases from baseline will be tabulated and graphically presented. *§calculate the mean and corresponding 95%CI of the log2 transformed values, back-transform this mean [ie 2mean] and CI [ie 2CI].* 

Actual values and fold changes from baseline are tabulated and shown as dot plots with dots for participant values, and the corresponding geometric mean and 95% CI per time point for each assay. In addition, Geometric Mean Titres (GMT) plots over time, combining the regimens in one graph (without individual participant dots) will also be created.

Reverse distribution curves of the actual values are provided for all time points.

In the graphs, original values will be displayed on the log2 scale.

Scatterplots with the VNA versus ELISA will be provided for the different time points. In these scatterplots the actual values will be shown, even if they are below the LLOQ, but the LLOQ cut-off will be visualized in the graph per assay if some values are below LLOQ.

For pre-F ELISA, the percentages of participants with 2- and 4-fold increase from baseline will also be tabulated.

GMT ratios and 95% CIs of all adults aged 18 to 59 years (Groups 1 and 3) versus adults aged 65 years and older (Group 5) and high-risk adults aged 18 to 59 years (Group 3) versus adults aged 65 years and older (Group 5) may be calculated for other VNA A2 timepoints and for other humoral assays, similarly to the primary endpoint.

Moreover, the difference in seroresponse rates for the same comparisons may be calculated for other VNA A2 timepoints and other humoral assays, similarly to the primary endpoint.

#### 5.5.1.2.2. Cellular assays

For **ELISpot** following results will be calculated: N, median, quartiles and range of the actual values will be tabulated and graphically presented.

Tables with the corresponding descriptive statistics will be provided.

Actual values are shown as box plots with dots for participant values, and the corresponding median and interquartile range per time point for each assay. In addition, box plots over time, combining the regimens in one graph (without individual participant dots) will also be created. For the graphs, original values will be displayed on the log10 scale.

For ICS and PBMC secreted cytokines (if available) possible analyses may include:

• Total Cytokine response: the % of subsets expressing at least IFN- $\gamma$ , TNF- $\alpha$ , or IL-2 will be calculated for CD4 and CD8.

Tables with the corresponding descriptive statistics will be provided.

Actual values are shown as box plots with dots for participant values, and the corresponding median and interquartile range per time point for each assay.

In addition, box plots over time, combining the regimens in one graph (without individual participant dots) will also be created.

- For all cytokine combinations (IFN-γ, TNF-α, or IL-2) bar charts reflecting the median magnitude of each combination will be graphically presented. Tables with the corresponding descriptive statistics will be provided.
- Th1 and Th2: Th1 is defined as %RSV-F specific CD4 T-cells IFNγ+ AND/OR IL2+ and Th2 as %RSV-F specific CD4 T-cells IL4+ AND/OR IL13+ AND CD40L+. Subject profiles and graphs of the actual values over time (box-plot type) will be created. In addition, at time points of interest, scatterplots of Th1 vs Th2 might be created.

For the graphs, original values will be displayed on the  $log_{10}$  scale.

Scatterplot with humoral and cellular assays may be provided for the most important time points.

Technical details for the calculation of the ICS values to be used in the graphs will be part of the DPS.

# 5.5.1.3. Immunogenicity Against the Vector

For Ad26-specific VNA following statistics will be calculated: N, geometric mean. §calculate the mean and corresponding 95%CI of the log10 transformed values, back-transform this mean [ie 10^mean] and CI [ie 10^CI]. and corresponding 95% CI of the actual values.

Participant profiles of the assays against the insert will be repeated, highlighting participants with pre-existing immunity at baseline against the vectors.

Scatterplots with the Adeno assays versus the assays against the inserts will be provided for all timepoints. In these scatterplots the actual values will be shown, even if they are below the LLOQ.

For the graphs, Ad26-specific VNA values will be displayed on the log10 scale.

# 5.6. Other Analyses

# 5.6.1. Definition of Subgroups

The following subgroups will be investigated for summary immunogenicity and safety analyses, for Cohorts 1 and 2 only:

• 18-49 years and 50-59 years

## 5.7. Interim Analyses

There is no interim analysis planned before the primary analysis.

# 5.7.1. Data Monitoring Committee (DMC) or Other Review Board

An IDMC will be installed to monitor the safety of participants in the ongoing phase 3 studies.

There are no planned IDMC reviews in the current study. Safety issues that might arise from this study may be escalated to an IDMC.

If a safety issue arises, the team might request an adhoc safety review by the IDMC. This review would be based on a snapshot of the database which might not have been completely cleaned. Data will be cleaned on an ongoing basis. The IDMC will review unblinded data; the data package to be reviewed (summary data) will display the real vaccine identity. The study team will transfer the blinded data to the statistical support group (SSG), and the IWRS vendor or Secure Data vendor will securely transfer the unblinded randomization data to the SSG. In principle there will be no meeting, unless this is requested by one of the IDMC members or by the Sponsor.

Conclusions from the IDMC reviews will be communicated to the Sponsor.

The IDMC data package (summary data) will follow the same statistical methods described in this SAP. Depending on the safety issue, the IDMC data package will consist of one or more of the following tabulations: participant disposition and demographics, SAEs, related SAEs, fatal AEs, related fatal AEs, solicited and unsolicited grade 3 AEs and related AEs. Potential AESI qualified for assessment will be listed. Other safety summaries might be requested as well. A separate IDMC DPS document will be provided to describe the specifications of the individual tables to be generated should a safety issue arise.

Data packages will be distributed by the SSG to the IDMC members via a secure electronic environment. A separate data package might be made available to the study team where the summary data are presented for the pooled groups (blinded).

The roles and responsibilities of the IDMC and SSG are detailed in the IDMC charter (Section 5).

